5.6 Data Analysis

5.6.1 Power/Sample Size:

This study is powered on weight and SF-12 PCS outcomes, using ANCOVA for 12-month follow-up weight adjusted for baseline weight, and applying a t-test for the 12-month SF-12 ⁷⁷. See Table 6 for a summary. A two-sided type I error rate of $\alpha = 0.025$ was chosen based on a multiple comparisons Bonferroni adjustment. In order to ensure adequate power for this pragmatic trial, we are enrolling 500 Veterans.

We based expected outcomes in D-ELITE on clinically meaningful outcomes. Regarding weight loss, we based it on the weight lost in E-LITE's self-directed arm among male participants (since we anticipate the majority of our Veteran participants will be male): 11 ± 2 lbs ⁶². This is an amount of weight loss likely to be clinically meaningful ³. We expect weight loss in the control condition to be similar to that achieved in the standard MOVE! program: 3.3 pounds ⁷⁸. Thus, we expect to be able to detect a 7.7-pound absolute difference in 12-month mean weight between treatment arms, which requires 78 patients per treatment arm (156 patients in total), assuming a 12-month weight standard deviation of 50 lbs ⁷⁹, correlation of 0.97 between baseline and 12-month weight, 90% power, two-sided Type I error rate $\alpha = 0.025$, and 20% attrition at 12 months ⁶². This scenario has a Cohen's d effect size of 0.154 ⁸⁰. A more conservative set of assumptions with a 6.7-pound difference (25% reduction in Cohen's d effect size) and a weaker correlation of 0.95 between baseline and 12-month weight measures requires 225 patients per treatment arm (450 patients in total) with all other assumptions unchanged.

For SF-12 PCS at 12 months, we assume a Minimal Clinically Important Difference (MCID) of a 5.00-point absolute mean difference for the SF-12 PCS ⁸¹ between treatment arms, with a standard deviation of 8.88 points based on unpublished E-LITE data, which corresponds to a Cohen's d effect size of 0.563 ⁸⁰. Also assuming 90% power, two-sided Type I error rate $\alpha = 0.025$, and 20% attrition at 12 months, this would require 100 patients per treatment arm (200 patients in total). A more conservative scenario that assumes a 4.33-point absolute mean difference (25%-reduced effect size) requires 176 patients per treatment arm (352 patients in total) with all other assumptions unchanged.

Table 6. Sample size requirements for 12-month weight, SF-12 PCS.

12-Month Outcome (Testing Method)	Significance Level	Power	Scenario Type	Mean Diff. (SD) Cohen's d	Sample Size (w/ 20% Attrition)	
					Per-Group	Total
Weight (ANOVA, with adjustment for baseline weight)	0.025	0.90	Mean Diff. = 7.7 SD = 50.0 Corr. b/w Baseline, 12-Mo. Measures = 0.97	7.7 (50.0) d = 0.154	78	156
			Conservative (25% Cohen's d reduction, Corr. = 0.95)	6.7 (57.7) d = 0.116	225	450
SF-12 PCS (t-test)	0.025	0.90	MCID = 5.00 SD = 8.88	5.00 (8.88) d = 0.563	100	200
			Conservative (25% Cohen's d reduction)	4.33 (10.25) d = 0.422	176	352

5.6.2 Retention:

As in other studies, we will carefully train and regularly review with staff best practices for retaining participants, including fully informed roles and responsibilities of staff and participants, and conveying an appreciation of participation and study identification. We will train staff to conduct effective informed consent to assure that participants fully understand the demands and nature of the study before they enroll. Coordinators will carefully review study requirements with participants, explain the concept of random assignment and what each treatment involves, and stress the importance of follow-up assessment even if they are not adhering to their assigned

treatment. We will use a database to systematically track participant activities, prompt the study team when action is required, and regularly produce quality control reports, all proven elements for participant retention.

5.6.3 Hypothesis Testing and Statistical Analyses:

We will use intention to treat (ITT) for all primary and secondary analyses. We will evaluate the dropout and missing data patterns for informative missingness⁸². To test for non-zero intervention effects on weight and SF-12 PCS, we will compare mean outcome between intervention and control groups at 12 month follow-up using the repeated-measures mixed-effects linear model:⁸³⁻⁸⁵

$$y_{ij} = \beta_0 + \beta_1(j) + \beta_2(\text{InterventionFollowUp}_{ij}) + \beta_3(\text{Age65Plus}_i) + \beta_4(\text{BMICat1}_i) + \beta_5(\text{BMICat2}_i) + \beta_6(\text{Urban}_i) + \alpha_i + e_{ij}$$

y_{ij} is the outcome (weight or SF-12 PCS) for patient i at baseline ($j = 0$) or 12-month follow-up ($j = 1$).

$\text{InterventionFollowUp}_{ij}$ is an indicator variable equal to 1 if patient i was randomized to the intervention arm and y_{ij} corresponds to a 12-month follow-up outcome ($j = 1$), and it is equal to 0 otherwise. Age65Plus_i is an indicator variable for whether the patient's age was at least 65 years at initial CDW pull. BMICat1_i is an indicator variable for whether the patient's BMI at initial CDW pull was ≥ 35 and < 40 , and BMICat2_i is an indicator variable for whether the patient's BMI at initial CDW pull was ≥ 40.0 and < 45 . Urban_i is an indicator variable for whether the patient's population density at initial CDW pull is urban. The adjustment for Age65Plus_i , BMICat1_i , BMICat2_i , and Urban_i is based on the use of these variables in our stratified randomization procedure.⁸⁶ The α_i are patient-level random effects, independently distributed $\text{Normal}(0, \sigma_\alpha^2)$. The e_{ij} are measurement-level errors, independently distributed $\text{Normal}(0, \sigma^2)$. Our primary weight and SF-12 PCS models do not adjust for the main effect of the intervention, and the coefficient estimates for $\text{InterventionFollowUp}_{ij}$ will serve as our treatment effect estimates. Our randomization is expected to promote equality across treatment arm with respect to our baseline outcomes and patient characteristics. Under this assumption, the coefficient for the main effect of treatment is expected to be zero, and our power is increased by excluding its estimation from our models.⁸⁷

We will adjust the co-primary outcome analyses for multiple testing using a Bonferroni adjustment,⁸⁸ which will allow for individualized assessment of our two primary outcomes at significance level 0.025 while maintaining a familywise error rate equal to 0.05. If exactly one hypothesis test leads to a null hypothesis rejection, we will infer that the intervention had a significant effect on that primary outcome but not the other. Two null hypothesis rejections and two failures to reject are also possibilities, in which case we will infer that the intervention had a significant effect on both or neither of our primary outcomes, respectively.

Exploratory analyses of Aim 2's biometric, psychological, and behavioral outcomes will be examined using tests of mean difference between groups after adjusting for baseline measures and randomization covariates in linear or logistic models, drawing on models used for primary analyses. We also will examine effects among women, and have estimated—with the assumptions of 80% power, ICC of 0.9, and 150 women participants—that we will have power to detect a similarly-sized effect among women as in the prior E-LITE trial.⁶² Given these outcomes are exploratory and are not focused on hypothesis testing, adjustment for multiple comparisons will not be performed.⁸⁹ Rather, these analyses will report effect sizes and 95% confidence intervals, along with p-values, to aid with interpretation of clinical significance.

5.6.4 Budget Impact Analysis:

To assess the economic impact of the intervention, we will focus on budget impact analyses to establish a business case for future implementation if the intervention is successful. We will perform a budget impact analysis from the VA perspective using a 12-month intervention period. First, we will compare costs of care potentially associated with weight loss therapies between the intervention and control groups: VA nutrition and behavioral weight management healthcare visits and weight loss medication from the VA Managerial Cost Account (MCA) System and Health Economic Resource System (HERC).^{90,91} Second, we will estimate potential future D-ELITE implementation costs, combining estimated potential patients based on trial reach

findings with costs of identifying and recruiting patients; training lifestyle coaches; and activities performed by the lifestyle coach using detailed project logs, incorporating data on staff salaries.⁹²

5.6.5 Misclassification and Missing Data:

We anticipate that any misclassification of outcome measurement will be non-differential with respect to randomization and effectively biasing our results toward the null. We will attempt to minimize misclassification by using approaches to decrease measurement error within the CDW data as well as by collecting patient-measured data when necessary. We will use data collected from primary care clinics preferentially. We will not collect weight data that was part of hospital admissions because of potential of changes in weight due to management. We will ask participants to use the scales provided only when not available in the CDW. If we find no evidence of informative missingness we will be able to rely on our use of well-specified mixed models to test effects of the intervention as these are known to lead to valid conclusions even when data are missing at random (MAR).^{87,93} If we detect informative missing data patterns, we will apply sensitivity analyses using pattern mixture models.⁸² Complete case analysis will only be performed as a sensitivity analysis, to provide useful inference if the data are mostly complete and the bias introduced by dropping the small proportion of incomplete cases is negligible.

5.6.6 Interim Analyses:

We plan no formal interim analysis of efficacy or futility. We will provide interim safety reports semi-annually to the Data Monitoring Committee (DMC).

5.7 *Withdrawal of Subjects*

We do not anticipate a need to withdraw a participant from the research entirely. If a participant becomes pregnant, we become aware of a serious physical or mental health issue, or the participant's primary care provider notifies us that the individual should not continue the intervention, the participant will cease participation in the intervention activities of the research; however we will continue to follow the individual through completion of the study via CDW and self-report.

If a participant chooses to withdraw him/herself from the research, we will confirm with the individual that we may continue to follow him/her in CDW. If the individual declines, we will respect his/her choice and not collect additional data from CDW; however we will use any data collected up to the date of withdrawal.

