In comparison to usual care, both self-directed lifestyle intervention and intensive coach-led group intervention produced comparable clinically significant weight loss over 2 years among adults who were overweight or obese with prediabetes and/or metabolic syndrome (**Figure 2**). This finding has important implications because weight regain is common in weight loss interventions, whereas weight loss maintenance for at least 2 years is a strong predictor of continued maintenance success.^{51,52} The self-directed intervention also led to significantly lower waist circumference and fasting plasma glucose, compared with usual care.¹⁵ A post-hoc analysis of E-LITE data found that mean (SD) change in the SF-12 physical component scores improved by 1.6 (4.7) in the self-directed intervention versus a decline of 0.4 (6.5) in the usual care control group ($p = .01$) and an increase of 0.7 (8.5) in the coach-led intervention ($p = 0.51$). In addition, increasing physical component scores were significantly correlated with weight loss in both interventions (**Figure 3**). The difference in physical component score change between the self-directed intervention and usual care (2.0; 95% CI, -0.1 to 4.0) was 4% of baseline (baseline M [SD], 50.5 [7.5]); 3% was the minimally important difference used in the DPP.⁵³ The SF-12 mental health scores changed slightly in both intervention

[figure not shown]

Figure 2. Estimated mean \pm SE weight change over a 24-month period, in kilograms (left y-axis) and as percentages (right y-axis), in the intention-to-treat population.

[figure not shown]

Figure 3. Correlation between changes in weight and SF-12 physical composite score (PCS) from baseline to 15 months.

groups and did not differ significantly from usual care. These findings are consistent with the DPP and other behavioral weight-loss intervention studies.⁵³⁻⁵⁵ They further demonstrate the favorable outcomes of the E-LITE self-directed intervention. As the first RCT that successfully translated the DPP-GLB lifestyle intervention into primary care in the U.S., E-LITE was cited as key evidence in the 2014 USPSTF behavioral counseling recommendations for CVD prevention in primary care.⁵⁶

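### Are the conservative sample-size scenarios in section 5.6.1 wrong because the prose omits Table 6's larger SDs, and does the 5.00-point PCS threshold clash with section 2.3.1?

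*Combined protocol and SAP*

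**What the plan says.** The prose of section 5.6.1 sets base cases of 7.7 lb (SD 50, baseline correlation 0.97) and 5.00 PCS points (SD 8.88). Both use 90% power, two-sided alpha 0.025 and 20% attrition. It then gives a conservative case for each outcome:

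- Weight: a "6.7-pound difference (25% reduction in Cohen's d effect size") with the correlation lowered to 0.95, which "requires 225 patients per treatment arm (450 patients in total) with all other assumptions unchanged".
- PCS: a "4.33-point absolute mean difference (25%-reduced effect size) requires 176 patients per treatment arm (352 patients in total) with all other assumptions unchanged".

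Table 6 prints these same scenarios as "6.7 (57.7) d = 0.116" and "4.33 (10.25) d = 0.422". The figure in brackets is the SD, and in each row it is larger than the SD in the prose.

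On the size of a PCS difference that matters, section 5.6.1 states that "we assume a Minimal Clinically Important Difference (MCID) of a 5.00-point absolute mean difference for the SF-12 PCS". Section 2.3.1, describing the predecessor trial, reports the difference in "physical component score change between the self-directed intervention and usual care (2.0; 95% CI, -0.1 to 4.0"), calls it clinically meaningful, and adds that "3% was the minimally important difference used in the DPP".

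**The concern.** Three things invite criticism.

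1. Someone who takes 6.7 lb and 4.33 points with the SDs in the prose and holds everything else fixed gets neither 225 nor 176. That looks like an arithmetic error in the justification for both co-primary outcomes, and it raises the question whether 500 is enough.
2. The document seems to hold two views of an important PCS difference: 5.00 points for planning, and 1.5 to 2.0 points in the background. With 200 completers per arm, an observed difference of about 2.0 points would already reach significance by t-test. A significant estimate between 2 and 5 points could then be called important or unimportant depending on the section cited.
3. The section never says what 500 can detect, and it sizes PCS with a t-test although section 5.6.3 analyses it with a model that includes baseline.

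If the first point were a true miscalculation, the trial might be underpowered for its own scenarios. If the second were a true contradiction, the reading of a co-primary result could be chosen after the fact.

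**Working it through.** **Inputs (section 5.6.1 and Table 6).** Two-sided alpha 0.025, power 0.90, attrition 20%; 1:1 allocation (section 5.3.3). z(0.9875) + z(0.90) = 2.241 + 1.282 = 3.523, and its square is 12.41.

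**Formulas.** Weight, per arm: n = 2 × 12.41 × SD² × (1 − r²) / difference² / 0.8. PCS, per arm: the two-sample t-test sample size divided by 0.8.

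**Base cases**
- Weight, 7.7 lb, SD 50, r 0.97: 2 × 12.41 × 2500 × 0.0591 / 59.29 / 0.8 = 77.3, so 78. Stated: 78.
- PCS, 5.00 points, SD 8.88: 80 / 0.8 = 100. Stated: 100.

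**Conservative cases with Table 6's SDs**
- Weight, 6.7 lb, SD 57.7, r 0.95: 2 × 12.41 × 3329.3 × 0.0975 / 44.89 / 0.8 = 224.4, so 225. Stated: 225.
- PCS, 4.33 points, SD 10.25: 141 / 0.8 = 176.25. Stated: 176 (strict rounding up gives 177).

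**Conservative cases with the SDs in the prose**
- Weight, 6.7 lb, SD 50, r 0.95: 168.5, so 169. d = 6.7 / 50 = 0.134, which is 13% below 0.154.
- PCS, 4.33 points, SD 8.88: 106 / 0.8 = 132.5, so 133. d = 4.33 / 8.88 = 0.488, which is 13% below 0.563.

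**How Table 6 builds the 25%.** The SD ratios are 57.7 / 50 = 1.154 and 10.25 / 8.88 = 1.154. The difference ratios are 6.7 / 7.7 = 0.870 and 4.33 / 5.00 = 0.866. Then 0.866 / 1.154 = 0.75. The square root of 0.75 is 0.866 and its reciprocal is 1.155, so the cut was shared equally between a smaller difference and a larger SD, in the same way for both outcomes. That is a deliberate construction.

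**Recovering the sample sizes from the prose alone.** The prose gives d, the 25% cut and the lowered correlation.
- PCS: 0.75 × 0.563 = 0.422; 141 / 0.8 = 176.25.
- Weight: 0.75 × 0.154 = 0.1155; 2 × 12.41 × 0.0975 / 0.1155² / 0.8 = 226.8. With d rounded to 0.116 it is 224.8, so 225.

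With the SDs kept at 50 and 8.88, a 25% cut in d means 5.775 lb and 3.75 points, and the sample sizes stay at about 227 and 176.

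**What 500 provides.** 500 / 2 × 0.8 = 200 completers per arm. The conservative cases need 225 × 0.8 = 180 (weight) and 141 (PCS). With 200 per arm, the differences detectable with 90% power are:
- Weight: 50 × √(1 − 0.97²) × √(2/200) × 3.523 = 4.3 lb in the base case; 57.7 × √(1 − 0.95²) × √(2/200) × 3.523 = 6.35 lb in the conservative case, below the 6.7 lb assumed.
- PCS by t-test: 3.1 points (SD 8.88) or 3.6 points (SD 10.25), below the 4.33 assumed. Power at 4.33 points with SD 10.25 is 0.976.

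**PCS thresholds side by side.** 3% of the predecessor's baseline of 50.5 is 1.5 points; 5.00 / 50.5 is 9.9%. The first is reported as the value another programme used, and the 2.0-point remark describes the predecessor's result. The 5.00 points is a planning value taken from a cited review. Section 5.6.3 tests each co-primary outcome at 0.025 and draws its conclusion from rejection or non-rejection. No threshold enters that rule.

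**The case for a change.** The strongest case for a change is that the prose is inaccurate as written. For PCS nothing but the difference is said to move, yet the SD moves as well. For weight the lower correlation is disclosed and the larger SD is not. It can be added that a co-primary outcome should have one importance threshold, fixed before results are seen. By the plan's own t-test, power at 2.0 points, which section 2.3.1 regards as meaningful, is only 50% (SD 8.88) or 38% (SD 10.25).

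The wording fault stands. A softer reading is available, since the scenarios are labelled by their cut in d, which contains the SD, and the unchanged assumptions could be power, alpha and attrition. Even so, the sentence would mislead someone who did not look at Table 6. But the prose directs the reader to that table, where both SDs appear.

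The threshold point stands only as advice on reporting. A trial may be planned on one published value while its background quotes another, and the documents do not show which is better supported. The 50% is also a lower figure than the planned analysis would give, because section 5.6.3 uses baseline PCS. With an assumed baseline correlation of 0.5 to 0.7 and SD 8.88, power at 2.0 points is 64% to 82%; the documents state no such correlation. Sizing PCS by t-test is therefore cautious.

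A statement of what 500 can detect would be convenient, but it follows from the printed inputs in one line.

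**Conclusion.** No change to the plan follows. The mismatch between the prose and Table 6 is clerical. The conservative effect sizes (0.116 and 0.422) are 25% reductions, and 225 and 176 per arm are right for the SDs in Table 6. The planned 200 completers per arm exceed the 180 and 141 needed. If the prose were taken literally instead, the requirement would fall to 169 and 133 per arm, so the slip cannot hide a shortfall. According to the Abstract, participants have been randomised and the 12-month questionnaires completed, so sample-size wording can no longer affect the design.

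The two PCS figures have different jobs, one for planning and one as background, and the decision rule in section 5.6.3 uses neither. A careful report will give the PCS estimate with its interval and discuss it against both values, without needing an amendment.

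These conclusions rest on the plan's own alpha, power, 20% attrition, SDs and weight correlations. Only the power range for PCS with baseline adjustment depends on an outside assumption, and the conclusion does not depend on it.

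### The primary mixed model forces equal variance at baseline and 12 months, so with model-based standard errors the 0.025 level is exact only if the two are equal; this matters mainly for SF-12 PCS

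*Combined protocol and SAP*

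**What the plan says.** Section 5.6.3 states the primary analysis of weight and SF-12 PCS: "we will compare mean outcome between intervention and control groups at 12 month follow-up using the repeated-measures mixed-effects linear model". Visit j = 0 is baseline and j = 1 is 12 months. The model is written out in full. The α_i "are patient-level random effects, independently distributed" with a single variance σ_α², and the e_ij "are measurement-level errors, independently distributed" with a single variance σ². The variance of the outcome is therefore σ_α² + σ² at both visits. The baseline means of the two arms are constrained to be equal, and the effect is the coefficient of the 12-month intervention indicator.

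Each co-primary outcome is then assessed "at significance level 0.025 while maintaining a familywise error rate equal to 0.05". On missing data, section 5.6.5 says that, without evidence of informative missingness, "we will be able to rely on our use of well-specified mixed models to test effects of the intervention". Sections 5.6.3 and 5.6.5 name no visit-specific variance, no unstructured covariance, no robust standard error and no check that the two variances agree.

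**The concern.** The treatment effect is a difference at 12 months, but the model computes its standard error from a variance pooled over both visits. If the 12-month variance is the larger, confidence intervals are too narrow and the test exceeds 0.025. If it is the smaller, the test is conservative. A larger sample does not cure either error.

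This is the confirmatory test, and section 5.6.3 draws a separate conclusion for each outcome, so a wrong level for PCS affects a stand-alone claim. Section 5.6.5 also rests validity under data missing at random (MAR) on the mixed model being correctly specified. With unequal variances the model implies the wrong regression of 12-month on baseline values, so dropout that depends on baseline and differs by arm also biases the estimate.

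**Working it through.** **Inputs.**
- Level: 0.05/2 = 0.025 two-sided, which reproduces the plan's figure; critical value 2.2414.
- PCS: section 5.6.1 plans "with a standard deviation of 8.88 points based on unpublished E-LITE data", without naming the visit. I take it as the 12-month SD, which is an assumption. It does reproduce Table 6: 80 completers per arm / 0.8 = 100.
- Section 2.3.1 gives a predecessor-trial baseline PCS SD of 7.5. It enters no sample-size calculation and is not shown to pair with 8.88.
- Weight: section 5.6.1 works "assuming a 12-month weight standard deviation of 50 lbs", with correlation 0.97 or, conservatively, 0.95. No baseline SD is given.

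**Algebra (complete data, 1:1 allocation).** Let s0 and s1 be the baseline and 12-month SDs given the strata, and c their covariance. The model fits the common variance a = (s0² + s1²)/2 and implies the slope b = c/a. The estimator is the arm difference at 12 months minus b times the arm difference at baseline. Up to the same sample-size factor:
- true variance: s1² − 2bc + b²s0² = s1²(1 − c²/a²)
- model variance: a − c²/a = a(1 − c²/a²)

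Hence reported SE / true SE = sqrt(a)/s1, and the actual level is 2(1 − Φ(2.2414 × ratio)).

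Example, 7.5 and 8.88: a = (56.25 + 78.85)/2 = 67.55; ratio = 8.219/8.88 = 0.926; level = 2(1 − Φ(2.075)) = 0.038.

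**PCS, s1 = 8.88:**

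| Assumed baseline SD | Level | 95% CI coverage |
|---|---|---|
| 7.0 | 0.044 | 92.2% |
| 7.5 | 0.038 | 93.0% |
| 8.0 | 0.033 | 93.8% |
| 8.5 | 0.028 | 94.5% |
| 8.88 | 0.025 | 95.0% |
| 9.5 | 0.020 | 95.8% |

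At 7.5/8.88 the SE is about 7% too small, and the familywise bound is 0.038 + 0.025 = 0.063, with weight at its nominal level.

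**Correlation (needed only for precision and simulation).** With SDs 7.5 and 8.88, the change SDs of 4.7 and 6.5 in section 2.3.1 (pooled 5.67) give r = (56.25 + 78.85 − 32.17)/(2 × 7.5 × 8.88) = 0.77. The interval −0.1 to 4.0 in the same section, with 81 per arm (section 2.3.2), gives a change SD of 6.66 and r = 0.68. The two sources disagree, so both are used. The precision loss at 7.5/8.88 is 1 to 2% in SE.

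**Simulation.** REML fits of the plan's mean model, N = 500, stratified 1:1, assumed stratum shares, 12,004 runs per setting, Monte Carlo SE about 0.0015 to 0.002. Rejection rates at 0.025:

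| Setting | Plan's model | Plan's model, sandwich SE | Unstructured |
|---|---|---|---|
| 7.5/8.88, complete, r = 0.77 | 0.038 | 0.026 | 0.026 |
| 7.5/8.88, complete, r = 0.68 | 0.037 | 0.024 | 0.025 |
| 7.5/8.88, 20% missing, unrelated to baseline, r = 0.77 | 0.038 | 0.026 | 0.026 |
| 7.5/8.88, 20% missing, unrelated to baseline, r = 0.68 | 0.041 | 0.027 | 0.027 |
| 7.5/8.88, one-arm MAR, log-odds 0.5 per SD, r = 0.77 | 0.045 | 0.031 | 0.028 |
| 7.5/8.88, one-arm MAR, log-odds 1.0 per SD, r = 0.77 | 0.056 | 0.039 | 0.028 |
| 7.5/8.88, one-arm MAR, log-odds 1.0 per SD, r = 0.68 | 0.048 | 0.032 | 0.026 |
| 8.88/8.88, 20% missing | 0.027 | 0.028 | 0.027 |
| 9.5/8.88, 20% missing, r = 0.68 | 0.022 | 0.029 | 0.028 |

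In the MAR rows 20% are missing and dropout is tied to low baseline PCS in one arm only. Bias under the plan's model is 0.11, 0.20 and 0.19 points in row order, against at most 0.01 in size for unstructured. The cause is the slope: at r = 0.77, c = 0.77 × 7.5 × 8.88 = 51.3, so the implied slope is 51.3/67.55 = 0.759 and the true slope 51.3/56.25 = 0.912.

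**Weight.** If the slope of 12-month on baseline weight, r × s1/s0, is at most 1, then s0 ≥ r × 50.
- r = 0.97: s0 ≥ 48.5 lb, ratio ≥ 0.985, level ≤ 0.027, precision loss at most 0.7%.
- r = 0.95: s0 ≥ 47.5 lb, ratio ≥ 0.975, level ≤ 0.029, precision loss at most 1.2%.

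These are marginal bounds. If the strata explained an assumed 30% of baseline weight variance, the levels would be 0.028 and 0.030.

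**The case against.** A random intercept with a common residual variance is a standard and fully specified choice, and no document shows unequal PCS variances in this trial. The 8.88 has no stated visit. The 7.5 comes from a different population, with prediabetes and/or metabolic syndrome and a PCS that section 2.3.1 calls normal at baseline. The 7.0 appears nowhere. Error control fails in one direction only: if the baseline variance is the larger, the test stays below 0.025. Sandwich standard errors, which the plan does not exclude, restore about 0.025 unless dropout depends on baseline. The MAR scenario is constructed, and its bias of 0.11 to 0.20 points is 2 to 4% of the 5.00-point MCID. Finally, the amendment log says the analysis section was aligned with a published protocol paper, so this would be a late change to a public primary analysis, and a sensitivity analysis might be enough.

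Much of this stands. Inflation is not demonstrated, its size rests on assumed SDs, weight is barely affected, and the MAR bias is small. It does not remove the point: the exact level depends on an equality that the documents do not establish and the analysis does not need. A robust standard error is not in the plan, and it would leave the wrong slope in place, with rejection at 0.031 to 0.039 under one-arm MAR dropout. A sensitivity analysis would leave the confirmatory test itself unchanged. The lateness is a reason to document the change properly.

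**Conclusion.** The concern holds. The algebra is certain: with model-based standard errors and complete data, the stated level and coverage are exact only if the two SDs, given the strata, are equal. The size and direction in this trial are not known in advance, because no document gives a baseline PCS SD for Veterans with BMI 30 to <45.

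For PCS the level is 0.044 to 0.020 over the assumed baseline SDs, and about 0.038 if 7.5 and 8.88 were the true pair. For weight it is close to nil. With complete data the estimate itself is unbiased. This should be fixed: the potential error in a confirmatory level is modest, and it can be avoided at almost no cost.

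**What to change.** Keep the constrained-baseline mean model and the estimand. For both co-primary outcomes, replace the random intercept plus common residual variance in section 5.6.3 with an unstructured 2×2 covariance for (baseline, 12 months), estimated by REML. Do not rely on sandwich standard errors alone, because they keep the misspecified covariance when 12-month data are missing at random.

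Document the change, with its reason, before any comparison by arm: the Abstract reports the 12-month questionnaires as completed. The currently specified model can be reported beside it as a sensitivity analysis.

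The cost is SAP wording and one extra variance parameter, with no new data or patients. If the variances are equal nothing material is lost: with both SDs 8.88 and 20% missing, the mean model SE was 0.566 under both structures, and the rejection rate was 0.0269 under the plan's model against 0.0271 unstructured.
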